13.2 Prior and Concomitant Medications

Concomitant medications will be coded using the World Health Organization (WHO) Drug Dictionary (Enhanced B2, March, 2016) and summarized to the therapeutic drug class (Anatomical Therapeutic Chemical (ATC) 4 classification) and preferred name. Medications with missing ATC codes will be classified as “uncoded”.

Concomitant medications are defined as those medications having been taken 1) prior to initiation of study drug administration and continuing for any period of time following the first administration of study drug or 2) at any time following the first administration of study drug and within 30 days of last dose.

14. Study Drug Administration, Extent of Exposure, and Dosing Compliance

14.1 Study Drug Administration

The number and percent of subjects who completed study administration will be summarized with the number and percentage of subjects in each treatment group and for all GBT440 using the Safety population. A subject will be defined to have “Completed Study Drug Administration” if the subject has a record for study drug administration corresponding to the Day-28 visit (Visit 6) and a response of “No” has been entered for the question, “Was study drug permanently discontinued?” on the Study Drug CRF for the same visit.

The number and percentage of subjects who permanently discontinued study drug, and the reason for discontinuation (adverse event (AE) or other) will be summarized by study drug and for all GBT440. The number and percentage of subjects who missed at least 1 dose of study drug, had at least 1 dose reduction, or had at least 1 dose interruption will be summarized by study drug and for all GBT440. The summary will include the number and percentage of subjects who had a dose reduction or dose interruption due to an adverse event. Additionally, the number and percentage of subjects grouped by number of doses missed, number of dose reductions, and number of dose interruptions will be summarized by study drug and all GBT440.

14.2 Extent of Exposure

Extent of treatment exposure for completed or discontinued subjects will be calculated in days using the following:

$$\text{Extent of Exposure (days)} = (\text{Date of last dose} - \text{date of first dose [Day 1]}) + 1 - (\text{Number of Missed Doses} + \text{Number of Days with Dose Interruption})$$

Extent of exposure (days) will be summarized with continuous descriptive statistics using the Safety population.

14.3 Dosing Compliance

Dosing compliance will be calculated using the following:

$$\text{Dosing Compliance (\%)} = \frac{\text{Sum of the Actual Days Dosed (days)}}{\text{Sum of Expected Days Dosed}} \times 100\%$$

The actual days dosed is defined as the sum of the days a subject was dosed. The number of expected days dosed that will be used for calculating dosing compliance will be calculated as (date of last dose – date of Day1 dosing +1) for all subjects, regardless of study completion status.

Dosing compliance will be summarized with continuous descriptive statistics for each treatment group, using the Safety population.

Study drug administration (including extent of exposure and dosing compliance) will be listed for all subjects who received at least 1 dose of study drug.

15. Primary Analysis

The primary endpoint in this study is treatment-emergent adverse events and tolerability. All safety analyses will be conducted using the Safety population.

15.1 Analyses of Treatment-emergent Adverse Events and Serious Adverse Events

TEAEs are defined as any event that occurs or worsens on or after the first dose of study drug and within 30 days after the last dose. Adverse events recorded in the eCRF which began prior to first dose of study drug will not be included in the summary tables but will be included in the AE data listings.

Adverse events reported for subjects participating in this study will be graded using the National Cancer Institute's (NCI) Common Terminology Criteria for Adverse Events (CTCAE), version 4.03. All AEs will be coded using the using MedDRA, version 19.0.

An overall summary will be presented that includes the number of TEAEs and the number and percentage of subjects who experienced at least one TEAE, by study drug and all GBT440. This summary will also include the number of Grade 3 or greater TEAEs, the number and percentage of subjects with at least 1 TEAE ≥ Grade 3, the number of possibly/probably related TEAEs, the number and percentage of subjects with at least 1 possibly/probably related TEAE, the number of serious adverse events (SAEs), the number and percentage of subjects with at least 1 SAE, the number of TEAEs leading to study drug discontinuation, the number and percentage of subjects who discontinued study drug due to TEAEs, and the number and percentage of deaths.

Additional summaries of TEAEs by study drug and all GBT440 will include the following:

- Incidence of TEAEs by SOC and PT

- Incidence of TEAEs by SOC and PT by antifibrotic use
- Incidence of TEAEs of Special Interest by SOC and PT
 - (If less than 5 events occur in each treatment group, then only a listing will be created)
- Incidence of TEAEs by SOC, PT, and Maximum Severity
- Incidence of TEAEs by SOC, PT, and Maximum Severity by antifibrotic use
- Incidence of TEAEs Resulting in Discontinuation of Study Drug
- Incidence of TEAEs Possibly/Probably Related to Study Drug
 - (If less than 5 events occur in each treatment group, then only listing will be created)
- Incidence of SAEs

All summaries will be provided showing the number and percentage of subjects who experienced at least one TEAE. TEAEs will be summarized using discrete summary statistics (number and percentage of subjects) and will be presented by study drug and total GBT 440 by SOC and PT. If a subject reports the same PT multiple times within the same SOC, that PT will only be reported once within that SOC. As with the PT, if a subject reports multiple conditions within the same SOC, that SOC will only be reported once. Summaries will list SOC in ascending alphabetical order, and PTs will be listed in order of descending frequency for all GBT440 subjects within each SOC.

Separate subject listings of AEs will be provided for all AEs, TEAEs Resulting in Discontinuation of Drug, SAEs, and Deaths.

15.2 Analyses of Other Safety Measures

15.2.1 Physical Examination

The physical examination results, height (cm), weight (kg), and body mass index (BMI) (kg/m²) will be summarized by study drug and all GBT 440 using summary statistics (number of subjects, mean, standard deviation, median, minimum, and maximum) by each applicable visit (Screening [Baseline], and Day 28,) in the Safety population. Height will be summarized only for Screening, and the screening height will be used for the calculation of BMI at Day 28. Weight collected at visits other than those specified in the protocol will be included in the summary for completeness. A subject listing of all physical exam results will be generated.

15.2.2 Vital Signs and Pulse Oximetry

Vital signs, including systolic blood pressure (SBP [millimeters of mercury (mmHg)]), diastolic blood pressure (DBP [mmHg]), heart rate (HR [beats per minute (bpm)]), respiratory rate (RR [bpm]), body temperature (degrees Celsius), and SpO₂ (%), will be summarized with continuous descriptive statistics at each visit by study drug and for all GBT 440 subjects in the Safety population. Change from baseline and percent change from baseline to each post-baseline visit also will be summarized.

15.2.3 Electrocardiogram (ECG)

HR (bpm), PR interval (milliseconds [ms]), QRS interval (ms), QT interval (ms), and QT interval with Fridericia's correction (QTcF [ms]) will be summarized using descriptive statistics by study drug and all GBT440 by visit in the Safety population. When all electrocardiogram (ECG) parameters, except for the QTcF interval, are collected at the site, the QTcF interval will be calculated using the following formula:

$$QTcF = QT / (60/HR)^{1/3}$$

Change from baseline to each post-baseline visit also will be summarized by study drug and all GBT 440. ECG triplicates will be averaged for summary tables. Each triplicate and the average of triplicates will be provided in a subject listing for Baseline, Day 8, Day 15, Day 28, Day 45, and Day 58.

Additionally, the number and percentage of subjects with QTcF > 450 ms, > 480 ms, and > 500 ms at baseline and as the maximum post-baseline measurement will be summarized. The number and percentage of subjects with maximum increase from baseline where increase in QTcF > 30 ms and > 60 ms will be included in the summary.

A subject listing of ECG parameters will include each triplicate and the average of triplicates for each visit.

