6.3. Study Treatment Discontinuation

Subjects should discontinue study drug for any of the following reasons:

- Malignancy: not including local and non-serious basal or squamous cell skin cancer
- Pregnancy
- Anaphylaxis, anaphylactoid or serious hypersensitivity reaction
- Use of any medication (refer to [Section 8.5](#)), intended to chronically treat IPF, other than those documented at screening
- Adverse event which in the opinion of the investigator precludes the subject from safely continuing in the study
- Pulmonary rehabilitation started at any time from screening until the end of the study
- Subject is noncompliant with study requirements

The date and reason for discontinuation should be documented in the eCRF.

Subjects who discontinue study drug should continue in the study to complete all scheduled assessments.

Those subjects who are unwilling or unable to complete all remaining study assessments, should return to the study site 2 weeks (+ 7 days) after the last dose of study drug to complete the Visit 8 (Day 45) assessments.

In this way all subjects will be assessed at least 5 half-lives after the last dose of study drug

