Note: All assessments should be performed within the number of days (Window) as indicated for each scheduled visit day. All assessments should be performed prior to receiving study drug during the treatment period unless otherwise indicated. SGRQ, ATAQ, UCSD, Cough VAS should be performed before all other non-PRO assessments, followed by 12-lead ECG and then vital sign assessments.

CONFIDENTIAL

- a All screening evaluations must be completed and reviewed prior to Day 1 (Visit 2) to confirm the subject meets all eligibility criteria prior to randomization to the treatment period. In cases when the screening 6MWT is done more than 7 days prior to Visit 2, it must be repeated, up and through Day 1, prior to any Day 1 assessments.
- b All subjects who discontinue study or study drug prior to study completion and who are unwilling or unable to complete the remaining scheduled visits should return to the study site to complete all Day 45 (Visit 8) assessments (refer to [Section 6](#))
- c Written informed consent must be obtained and documented prior to performing any study-specific screening procedure
- d Demographics, medical history and baseline conditions obtained at screening should be reviewed again at this visit and any changes since screening updated in the eCRF
- e Includes evaluation of the head, eyes, ears, nose and throat and cardiovascular, respiratory, musculoskeletal, gastrointestinal, neurological, dermatologic systems. No rectal or pelvic examination is required. Record any observed abnormalities in the eCRF. At subsequent visits record new or worsened clinically significant findings on the eCRF
- f Perform a limited, symptom-directed examination as clinically indicated. Record new or worsened clinically significant findings in the eCRF.
- g Includes heart rate, respiratory rate, systolic and diastolic blood pressure and temperature measured whilst in a semi-recumbent or supine position and resting for at least 5 minutes.
- h Performed while the subject is seated and resting for at least 5 minutes.
- i Perform 12-lead ECG in triplicate; three separate tracings with approximately 1 minute between each tracing, after resting in a semi-recumbent or supine position for at least 5 minutes.
- j After informed consent but prior to randomization only serious adverse events (SAEs) resulting from a protocol-mandated intervention should be reported. After randomization, all adverse events will be reported until study completion (Day 58).

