10.3 Data Analysis Conventions

Analyses for SMC meetings, interim analyses, and final data analysis will be performed by Statistics & Data Corporation (SDC). The final data analyses will be performed after Part B of the study is completed and the database has been locked. Data from Parts A and B of the study will be pooled across the common treatment arms (GBT440 600 mg and placebo arms). Statistical programming and analyses will be performed using SAS® Version 9.4 or higher. All study data will be listed by subject, study drug,

and visit (as applicable) based on randomized and treated subjects unless otherwise specified. Summary statistics will be presented by treatment group including all GBT440, and will include a total column where appropriate.

Study visits will be referred to in all tables and listings as the visit name corresponding to the planned study visit.

Summaries for continuous and ordinal variables will include the number of observations (n), arithmetic mean, standard deviation (SD), median, minimum, and maximum). Minima and maxima will be reported with the same precision as the raw values; means and medians will be presented to one additional decimal place than reported in the raw values. Standard deviations will be presented to two additional decimal places than reported in the raw values. Summaries for discrete variables will include frequency counts and percentages. All percentages will be rounded to one decimal place (i.e., XX.X%).

All statistical tests will be two-sided with a significance level of 0.05 ($\alpha = 0.05$) unless otherwise specified. Confidence intervals (CI) for differences between treatment groups will be two-sided at 95% confidence. All p values will be rounded to four decimal places; p-values less than 0.0001 will be presented as “<0.0001”; p-values greater than 0.9999 will be presented as “>0.9999”.

All summary tables will be supported with subject listings.

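### The QTcF outlier counts use the maximum over all post-baseline ECGs, so off-drug Day 45 and Day 58 readings add noise and slightly dilute any on-drug difference

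*SAP*

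**What the plan says.** SAP 15.2.3 plans one categorical QTcF summary. The number and percentage of subjects above 450, 480 and 500 ms are given "at baseline and as the maximum post-baseline measurement will be summarized", with the number whose maximum increase from baseline exceeds 30 or 60 ms. Triplicates are averaged for tables. No cut-off by time since last dose is stated for either count.

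The same section provides a "subject listing for Baseline, Day 8, Day 15, Day 28, Day 45, and Day 58", so there are five scheduled post-baseline ECGs. Dosing lasts 28 days. Protocol Appendix A allows ±2 days at Day 28 and ±3 days at Days 45 and 58.

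Protocol 6.3 says: "Subjects who discontinue study drug should continue in the study to complete all scheduled assessments". Those who will not or cannot do so should "return to the study site 2 weeks (+ 7 days) after the last dose of study drug", followed by: "In this way all subjects will be assessed at least 5 half-lives after the last dose of study drug".

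QTcF and its change are also summarized by visit. Under SAP 10.3, continuous summaries include the "arithmetic mean, standard deviation (SD), median, minimum, and maximum". SAP 15.1 counts adverse events as treatment-emergent if they fall "within 30 days after the last dose".

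**The concern.** A subject's maximum over five ECGs is at least as large as the maximum over the three taken during dosing. If the last two carry almost no drug, they can only add chance excursions, in GBT440 and placebo arms alike. The placebo rate then rises by more than the rate in an arm with a real on-drug effect, where many subjects have already been counted, so the difference shrinks.

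Safety is the primary endpoint, and this is the only table that counts QTcF outliers. Protocol 1.3 describes multiple-dose experience of 300 to 1000 mg, and Part B adds 1500 mg. After pooling the common arms, each arm has 6 to 9 subjects, so one follow-up excursion moves an arm's percentage by 11 to 17 points (1/9 to 1/6). The table would not show that it happened off drug. Subjects who stop early but stay on the visit schedule add further off-drug ECGs.

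**Working it through.** The documents give no QTcF rate or power figure to reproduce. The check covers timing, residual drug, and the effect of three versus five ECGs.

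**Timing (Appendix A windows).** A completer's last dose falls on Day 26 to 30, the Day 45 visit on Day 42 to 48, and the Day 58 visit on Day 55 to 61.
- Day 45: 42 − 30 = 12 to 48 − 26 = 22 days after the last dose.
- Day 58: 55 − 30 = 25 to 61 − 26 = 35 days.

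**Residual drug.** Protocol 6.3 treats a visit 14 days after the last dose as at least 5 half-lives out, so the half-life h is at most 14/5 = 2.8 days. Protocol 3.1 describes the 30-day follow-up as at least 5 half-lives, which bounds h only at 30/5 = 6 days. Both are inferred bounds, not PK estimates. The fraction remaining is 2^(−t/h):

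| Days since last dose | h = 2.8 | h = 6 |
|---|---|---|
| 5 | 29% | 56% |
| 11 | 6.6% | 28% |
| 12 | 5.1% | 25% |
| 17 (nominal Day 45) | 1.5% | 14% |
| 18 | 1.2% | 12.5% |
| 30 (nominal Day 58) | 0.06% | 3.1% |

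**Chance of a maximum increase above c.** Assume one baseline ECG visit, k independent post-baseline visits, and the same SD σ of the triplicate mean at each. Then

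P = 1 − ∫ φ(b) Φ(c/σ + b)^k db.

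For an on-drug shift δ at Days 8, 15 and 28 only, the integrand over five ECGs becomes φ(b) Φ((c − δ)/σ + b)^3 Φ(c/σ + b)^2. The documents give no σ; 8, 10 and 12 ms are assumed. With c = 30 ms and δ = 10 ms (also assumed):

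| | σ = 8 | σ = 10 | σ = 12 |
|---|---|---|---|
| No effect, 3 ECGs | 1.10% | 4.36% | 9.35% |
| No effect, 5 ECGs | 1.71% | 6.47% | 13.33% |
| Extra cases in 24 GBT440 subjects | 0.15 | 0.51 | 0.96 |
| Extra cases in 9 placebo subjects | 0.05 | 0.19 | 0.36 |
| +10 ms on drug, 3 ECGs | 9.35% | 17.72% | 25.39% |
| +10 ms on drug, 5 ECGs | 9.62% | 18.67% | 27.27% |
| Difference from placebo, 3 → 5 ECGs (points) | 8.2 → 7.9 | 13.4 → 12.2 | 16.0 → 13.9 |
| Ratio to placebo, 3 → 5 ECGs | 8.5 → 5.6 | 4.1 → 2.9 | 2.7 → 2.0 |

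The 24 and 9 come from the planned arm sizes: 600 mg 6 + 3, 900 mg 6, 1500 mg 9; placebo 6 + 3.

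**Other rows, no drug effect, 3 v 5 ECGs.**
- Above 60 ms, largest case (σ = 12): 0.06% v 0.10%.
- Above 450 ms, by simulation (subject means normal, 425 ms, SD 12; baseline at most 450 ms; σ = 10): 9.5% v 13.5%.
- Above 480 ms, largest case tried (mean 435 ms, σ = 12): 0.36% v 0.58%.

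The simulation applies the male eligibility limit to everyone, which is a simplification.

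**General form.** If each off-drug ECG exceeds a threshold independently with probability p0, the difference over five ECGs equals the three-ECG difference times (1 − p0)^2. That factor is 0.98, 0.90 or 0.81 for p0 of 1%, 5% or 10%. It is below 1 whenever off-drug excursions occur.

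**The case against.** The other side is fair on several points.

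- **Maximum post-baseline is a legitimate worst-case display.** It matches the 30-day adverse-event window, which nominally reaches Day 58. This stands, and is a reason to keep an overall column.
- **The on-drug picture is largely recoverable.** If an arm's by-visit maximum change at Days 8, 15 and 28 is at most 30 ms, there are no on-drug cases. Otherwise the listings date each one. This stands in part: by-visit maxima do not give a number of subjects, and dating cases by hand is not a prespecified summary.
- **The shift is below the data's resolution.** A change of 0.3, 1.2 or 2.1 points compares with a standard error of about 7, 11 or 15 points for 24 versus 9 subjects. With 9 placebo subjects, the chance of no on-drug placebo case at all is 91%, 67% or 41%, so the ratios above often could not be observed. No hypothesis is tested. All of this stands, and keeps the point minor.
- **Off-drug status is inferred.** At a 6-day half-life, 14% of drug would remain at nominal Day 45. This stands as a limitation.
- **Protocol 6.2 allows an early Visit 8.** Subjects who leave the study may have that ECG about 7 days after the last dose. This does not defeat the split, which goes by actual days since last dose, so such an ECG counts as on-treatment.
- **Any cut is somewhat arbitrary.** Day 11 and Day 12 differ little in residual drug. True, but 11 days is tied to the visit windows and places every completer's on-schedule Day 45 ECG in follow-up.

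**Conclusion.** The concern holds as a small, optional improvement. The QTcF counts have no on-treatment window, and two of five scheduled ECGs are off drug or nearly so by the protocol's own half-life statement. The added noise is shared by all arms, so there is no bias against GBT440, only dilution and loss of timing.

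For increases above 30 ms, the assumed SDs of 8 to 12 ms and a 10 ms on-drug effect give a loss of 0.3 to 2.1 points, about 4% to 13% of the difference. That is less than one extra false case among 24 GBT440 subjects. The >450 ms row is also affected; the >60, >480 and >500 ms rows hardly are.

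These sizes depend on the assumed SD, QTcF means and drug effect, on independence between visits, and on no drug effect at Days 45 and 58. The missing window itself does not depend on them.

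**What to change.** In SAP 15.2.3, split the threshold and maximum-increase counts by actual days since last dose:

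1. **On-treatment:** ECGs after the first dose through 11 days after the last dose. Eleven days is shorter than both the 12-day minimum gap to a completer's Day 45 visit and the 14-day visit in Protocol 6.3.
2. **Follow-up:** every later ECG, with the same thresholds, including later scheduled visits of subjects who stopped drug early.

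Each post-baseline ECG then falls in exactly one column. For a subject who stops on Day 10, the Day 15 ECG (5 days off, about 29% left at a 2.8-day half-life) is on-treatment and the Day 28 ECG (18 days off, about 1%) is follow-up. The present overall column can stay beside these.

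The cost is two sentences in the SAP and one or two table columns, with no new data or procedures and no ECG dropped. The drawback is that at a half-life near 6 days about 28% of drug remains at the cut, so some follow-up ECGs would still carry exposure. The overall column covers that case. If the separate PK analysis shows a longer half-life, report it as a limitation of the split.

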15.2.4 Clinical Laboratory Results

Clinical laboratory data including serum chemistry, liver function tests, serum hematology, serum erythropoietin, coagulation panel, and urinalysis are collected at specified visits. The quantitative variables will be summarized by study drug and all GT440 with continuous descriptive statistics for each visit in the Safety population. Urinalysis results will be presented only as a subject listing. Change from baseline and the percent change from baseline will also be summarized by study drug and all GBT 440. Units for laboratory results will be converted from reported units to SI units in the SDTM datasets. Reported results and units will be used for the summary tables.

Subject listings of laboratory data will include a separate listing for clinically significant laboratory values in addition to subject listings of all laboratory values. Listings will be presented with reported units and SI units. Pregnancy test results for both serum and urinalysis sampling will be provided in a separate listing.

16. Secondary Analyses of 6-Minute Walk Test

The 6-Minute Walk Test is a multiple period assessment that includes a resting period (first minute before the walking portion), the 6-minute walking period, and a post-walking period that includes results at each minute for 2 minutes upon completion of walking. End of exercise is defined as last SpO₂ immediately at end of 6MWT (not including the post-walking period). Blood pressure is collected at rest

and at each minute post walking. The distance walked (meters) is recorded at the end of the walking period.

Results of the 6-Minute Walk test (6MWT) will be summarized by study drug and all GBT440 at the following visits: Baseline (Screening or repeat at Day 1 if applicable), Day 15, Day 28, and Day 58. The number and percentage of subjects in each treatment group and all GBT 440 who completed the 6MWT, experienced myocardial infarction (MI) or unstable angina in the previous 30 days before the 6MWT, and utilized oxygen during the 6MWT will be summarized. Summary statistics (N, mean, SD, median, min, and max) will be displayed for systolic and diastolic blood pressure collected at rest and at each minute post-walking.

Subject listings will be provided for all 6MWT data collected on the eCRF.

Summary statistics for resting SpO₂, SpO₂ at end of the 6MWT (last available result) and lowest SpO₂ collected during the 6MWT will be summarized at each visit by study drug and all GBT440 in the Efficacy-Evaluable population. Summary statistics for the change and percent change from baseline to Day 15, Day 28, and Day 58 also will be displayed.

Analysis of covariance models (ANCOVA) will be used to analyze the effect of treatment on the change from baseline and the percent change from baseline for each secondary endpoint with baseline value as a covariate. Least squares (LS) means and SEs will be displayed for the change and percent change from baseline in each treatment group and for all GBT440.

LS means (95% CI) and p-values from the models will be used to make the following comparisons:

- GBT440 600 mg – Placebo
- GBT440-900 mg – Placebo
- GBT440-1500 mg – Placebo
- All GBT 440 – Placebo

17. Exploratory Analyses

17.1 6-Minute Walk Test

Summary statistics for the distance walked (meters) during the 6MWT, time to the first SpO₂ < 88%, and AUC of SpO₂ will be summarized by study drug and all GBT 440, and visit in the Efficacy-Evaluable population. The change and percent change from baseline to Day 15, Day 28, and Day 58 in distance walked also will be summarized and displayed.

The AUC of SpO₂ measurements will be calculated for each subject's data at baseline, Day 15, Day 28, and Day 58. The AUC will be estimated using the trapezoid rule for data collected on the eCRF as follows:

$$AUC = \left\{ \sum_{t=1}^n \frac{1}{2} [(Time_t - Time_{t-1}) \times (SpO2_t + SpO2_{t-1})] \right\}$$

where n is the number of measurements of SpO₂ collected during the 6MWT, t is the elapsed time in minutes (nominal time) and SpO₂ is the measurement of SpO₂ level at the respective timepoint, and Time is the timepoint. If a SpO₂ measurement is missing during the 6MWT, then that timepoint is removed from the calculation, such that the AUC is calculated using the trapezoid rule from the 2 timepoints surrounding the missing SpO₂ measurement.

Additional exploratory endpoints include the change from rest to end of 6MWT and change from rest to lowest SpO₂. Both endpoints will be summarized by study drug and all GBT440.

ANCOVA models will be used to analyze the effect of treatment on the change from baseline for each exploratory endpoint with baseline value as a covariate. Least squares (LS) means and SEs will be displayed for the change from baseline in each treatment group and for all GBT440. Similar ANCOVA models will be constructed for percent change from baseline for AUC and distance walked.

LS means (95% CI) and p-values from the models will be used to make the following comparisons:

- GBT440 600 mg – Placebo
- GBT440-900 mg – Placebo
- GBT440-1500 mg – Placebo
- All GBT 440 – Placebo

All exploratory efficacy data will be provided in subject listings.

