--	--

Number of Subjects	
In Part A, a total of approximately 18 subjects will be randomized 1:1:1 to either: 900 mg GBT440, 600 mg GBT440 or placebo.
 
In Part B, up to an additional 15 subjects will be randomized 3:1:1 to either: 1500 mg GBT440, 600 mg GBT440 or placebo.

Replacement of Subjects	
Subjects who do not complete at least 10 days of dosing for reasons unrelated to toxicity may be replaced.

Number of Centers	
The study will be conducted at approximately 10–15 clinical sites in the United States

Duration of Study Participation	
Approximately 79 days, including screening, treatment and follow-up periods

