5.4. Laboratory Examination

5.4.1. Clinical Laboratory Studies

It is the responsibility of the Investigator to assess the clinical significance of all abnormal clinical laboratory values as defined by the list of normal values on file for the local clinical

laboratory. All clinically significant laboratory value abnormalities are to be recorded as AEs.

For the purpose of this study, a clinically significant laboratory value will be any abnormal result that, in the judgment of the Investigator, is an unexpected or unexplained laboratory value or if medical intervention or corrective action is required. Any abnormal values that persist should be followed at the discretion of the Investigator.

Please refer to [Appendix A](#) Schedule of Study Assessments for all time points.

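### Laboratory summary tables use units as reported by local laboratories, with no common-unit rule, although standardized values are already planned

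*SAP*

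**What the plan says.** SAP 15.2.4 (Clinical Laboratory Results) covers chemistry, liver function, hematology, erythropoietin and coagulation. Three of its sentences concern units:

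- Data: "Units for laboratory results will be converted from reported units to SI units in the SDTM datasets".
- Tables: "Reported results and units will be used for the summary tables".
- Listings: "Listings will be presented with reported units and SI units".

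The quantitative variables are summarized by study drug and for all GBT440 "with continuous descriptive statistics for each visit in the Safety population". In addition, "Change from baseline and the percent change from baseline will also be summarized by study drug and all GBT 440". SAP 10.3 specifies n, mean, SD, median, minimum and maximum, and pools the 600 mg and placebo arms across Parts A and B.

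On the source of the results, Protocol 5.4.1 has the investigator judge abnormal values against "the list of normal values on file for the local clinical" laboratory. The Protocol Synopsis (Number of Centers) says: "The study will be conducted at approximately 10–15 clinical sites in the United States".

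**The concern.** The plan creates a common scale and then leaves it out of the only laboratory outputs that average over subjects. SI values appear in the listings, where nothing is averaged. With local laboratories at several sites and no stated common unit, an arm mean is meaningful only if every laboratory contributing to it happens to report that analyte in the same unit.

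Protocol 11.2.1 counts laboratory evaluations among the measures by which safety, the primary objective, is assessed. Protocol 1.5.4.1 names tissue hypoxia as a theoretical risk and monitors it through erythrocytosis, resting heart rate, erythropoietin and laboratory tests of organ injury such as aminotransferases. All of these except heart rate come from laboratory results. The arms are small, so one subject on a different scale carries great weight in a mean or SD.

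**Working it through.** The plan gives no figure to reproduce on this point. The check is first of the text, then an illustration of size.

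**Text.** The conversion to SI and the use of reported units in tables stand in consecutive sentences, so the table rule is explicit. Neither document contains a central safety laboratory, a standard unit per analyte, a step that harmonizes units before summarizing, or a rule that splits a table row by unit.

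**Arm sizes (Protocol 3.1; SAP 4 and 10.3).** 900 mg: 6. 1500 mg: 9. Pooled 600 mg: 6 + 3 = 9. Pooled placebo: 6 + 3 = 9.

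**Assumptions, not from the documents.** Every subject has a baseline hemoglobin of 14 g/dL and a true rise of 0.5 g/dL. In an arm of n subjects, k have results reported in g/L, a factor f = 10.

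**Formulas.**

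- Arm mean = [(n − k) × 14 + k × 140] / n
- Mean change = [(n − k) × 0.5 + k × 5] / n
- Both equal the true value times 1 + k(f − 1)/n.

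For n = 9, k = 1: mean = (8 × 14 + 140)/9 = 252/9 = 28.0; mean change = (8 × 0.5 + 5)/9 = 9/9 = 1.00.

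For n = 6, k = 1: mean = (5 × 14 + 140)/6 = 210/6 = 35.0; mean change = (5 × 0.5 + 5)/6 = 7.5/6 = 1.25.

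| n | k in g/L | Mean | SD | Mean change | Mean % change |
|---|---|---|---|---|---|
| 6 | 0 | 14.0 | 0 | 0.50 | 3.57 |
| 6 | 1 | 35.0 | 51.4 | 1.25 | 3.57 |
| 6 | 2 | 56.0 | 65.1 | 2.00 | 3.57 |
| 6 | 3 | 77.0 | 69.0 | 2.75 | 3.57 |
| 9 | 0 | 14.0 | 0 | 0.50 | 3.57 |
| 9 | 1 | 28.0 | 42.0 | 1.00 | 3.57 |
| 9 | 2 | 42.0 | 55.6 | 1.50 | 3.57 |
| 9 | 3 | 56.0 | 63.0 | 2.00 | 3.57 |

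**Percent change.** SAP 10.2 computes it within subject, so the unit cancels: 0.5/14 = 5/140 = 3.57%. It fails only if a subject's unit differs between visits. For example, 14 g/dL followed by 145 g/L gives (145 − 14)/14 = 936%.

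**With one unit throughout.** The same arm gives a mean of 140 g/L and a mean change of +5 g/L, whichever unit each laboratory used. When all sites already agree (the k = 0 rows), the fix alters only the unit displayed, and nothing at all if the agreed unit is chosen.

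**The case against.** The strongest reply is that the table sentence is a presentation choice. All sites are in one country, and the protocol's own examples are in conventional units: hemoglobin per deciliter in exclusion criterion 8, potassium in mEq/L in Protocol 10.5.4. On that reading the tables simply show conventional units and the SI values sit in SDTM and the listings. A reader might infer from the SAP that values in unlike units will be averaged. The documents do not support that: they show no difference in units between sites, and the eCRF's accepted units are not among them. This stands, and it makes the point conditional. It does not remove it, because the rule as written contains nothing that secures a common unit.

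A reader might also infer that mixed units would hide or create a safety signal. That goes too far. In the arm of 9 with one value in g/L, the median stays at 14 while the maximum is 140, so the table itself shows the problem. Every summary table is backed by listings (SAP 10.3), the laboratory listings carry both sets of units, and clinically significant values have their own listing (SAP 15.2.4). Out-of-range values are flagged (Protocol 11.3.1). Investigators judge abnormalities against local normal values, and significant ones become adverse events (Protocol 5.4.1), without reference to arm means. Edit and validation checks precede the final analysis (SAP 8). No hypothesis test on laboratory values is planned. All of this stands. Two limits remain: by the formula above, a conversion factor nearer 1 distorts the mean less but is also harder to notice; and correcting a mixed table after the fact would mean departing from the SAP.

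Finally, SI units are not essential. A single conventional unit per analyte does the same work, and that is accepted in the fix.

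**Conclusion.** The point holds in a limited, conditional form. Followed literally, SAP 15.2.4 lets arm means, SDs and absolute changes for an analyte combine scales whenever one contributing laboratory uses a different unit. In arms of 6 to 9 a single such subject is enough to make those statistics meaningless: for an assumed tenfold unit difference the mean and mean change are multiplied by 2.5 in an arm of 6 and by 2 in an arm of 9. Percent change is safe unless a subject's unit changes between visits.

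This rests on two things: that the laboratories are local, as Protocol 5.4.1 indicates, and that at least one reports an analyte differently, which the documents do not show. If units agree, there is no error. The consequence is confined to descriptive tables that support the primary safety objective. Counts of treatment-emergent adverse events and the SpO₂ analyses are not affected. It is worth correcting because the correction is nearly free, not because harm has been demonstrated.

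**What to change.** In SAP 15.2.4, replace the sentence on summary tables with:

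> Summary tables will use one standard unit per analyte, derived from the standardized SDTM results (SI, or a single pre-specified conventional unit).

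Keep reported and SI units in the listings as planned. If conventional units are preferred for readability, add a short list giving the unit chosen for each analyte.

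The cost is one SAP sentence. The conversion is already specified, and SAP 8 already routes all summary-table data through analysis datasets. No new data, visits or subjects are needed.
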